Overview. At baseline, we will obtain self-report measures (see below), height and weight, a blood sample for A1C, and accelerometer data for physical activity. At each intervention phone session, interventionists will collect feasibility and acceptability data (see below). At the follow-up visit (8 weeks), a blinded assessor will obtain repeat self-report data, vitals, A1C, and accelerometer data. At 16 weeks, a blinded assessor will obtain self-report data by telephone, and an accelerometer will be mailed to the participant to measure physical activity. All participants will receive pedometers, free parking or public transportation at all visits, \$20

after the second visit, \$40 after the 8-week follow-up visit, and \$40 after the 16-week phone assessment, after all devices have been returned.-

Initial/Enrollment Visit (in-person visit #1). We will collect data on basic sociodemographic variables (age, gender, race/ethnicity, living alone, duration of T2D, medical/psychiatric comorbidities, medications) needed to characterize our population (and to be used as part of randomization by minimization). Next, participants will complete self-report measures, and we will draw blood for A1C if participants did not have these procedures completed as part of a clinical visit (if they had A1C in the last 3 weeks, including this visit, we will use that value to prevent subjecting participants to the blood draw). This visit will occur on site, partially in offices in the Warren building and partially in the MGH Corrigan Minehan Heart Center. Finally, participants will be given an accelerometer, which will be worn over the subsequent week (prior to visit #2) to measure baseline physical activity.

Objective physical activity assessment and in-person visit #2. In order to gather baseline physical activity data, participants will take home and wear accelerometers for 1 week prior to visit #2. During in-person visit #2, participants will return their accelerometers and will begin the study intervention, as outlined below.

Intervention (PP-MI vs. MI alone: 8 weekly phone sessions).

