PP-MI intervention. Participants randomized to PP-MI will receive a treatment manual. For each session, a PP exercise will be described in the manual, with instructions and space to write about the exercise and its effects. Next, an MI section will outline specific MI-based topics (e.g., pros/cons, managing slips) and facilitate physical activity goal-setting. Following randomization (in-person visit #2), interventionists will introduce PP exercise #1 and MI session #1 to participants to aid engagement. Following visit #2, participants will engage in weekly, 30-minute phone calls for the next 8 weeks. Participants will independently complete PP exercises and MI-based goals between phone sessions and review them during phone sessions over 8 weeks. PP and MI components will be delivered stepwise within sessions (rather than intertwined) based on our experience, participant feedback, and pilot work.

PP component details. The PP portion of phone sessions (15 mins) will be structured to include: (i) review of the prior PP exercise, (ii) discussion about how to translate the PP exercise skills to daily life (e.g., related to physical activity goals or other activities), including a specific focus on how such skills can be used to foster social support and interactions, and (iii) assignment of the next exercise via guided review of the treatment manual.

Session 1: Counting blessings ⁶¹	Participants recall three events, small or large, in the preceding week that were associated with satisfaction, happiness, pride, or other positive states
Session 2: Gratitude letter ²⁴	Participants write a letter of gratitude thanking a person for their support or kindness.
Session 3: Enjoyable and meaningful activities ⁶⁴	Participants complete three activities: an enjoyable activity alone, an enjoyable activity with another person, and a meaningful activity completed alone or with others.
Session 4: Implementation	Participants focus on implementing positive psychology skills into daily life.
Session 5: Recalling past success ⁶³	Participants recall an event in which they experienced success. They next write about the event, their contribution to the success, and positive feelings elicited by recalling it.
Session 6: Using personal strengths, part 1 ²⁴	Participants identify a signature strength, then find a specific new way to use that strength in the next 7 days.

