Barriers to and Resources for Activity (*Session 6*)

Participants will identify barriers to physical activity in their life and brainstorm ways to problem-solve around those barriers. Furthermore, they will identify social, community-based, and equipment resources available to help them with physical activity.

Part Four: Having a Healthy Diet

Making Dietary Changes (*Session 7*)

Participants will learn about the importance of reducing sugar, fat, and cholesterol in their diet. Next, they will identify one way in which they wish to change their diet. They will discuss the importance of making the change and their confidence about being able to do so. Finally, they will create a list of pros and cons for behavior change.

Barriers to and Resources for a Healthy Diet (*Session 8*)

Participants will review how to properly read a food label and learn techniques to make healthy decisions while food shopping. They also will identify barriers to a healthy diet, problem-solve those barriers, and identify resources that can help to improve their diet.

Planning for the Future (*Session 9*)

Participants will review the information learned over the course of the program and think of ways to remain healthy after the end of the program.

Follow-up assessments (weeks 8 [in-person] and 16 [by phone]). After completion of the intervention, participants will wear the Actigraph accelerometers for 1 week (they will have had the devices [which have no identifying information outside of a serial #] mailed to them prior to the visit and will return them at the in-person session), then return to the TCRC for an in-person session (8 weeks). At this session, height and weight, hemoglobin A1c, and self-report data will be obtained. These visits will occur on the MGH main campus (TCRC). At 16 weeks, a follow-up phone session will be performed to obtain self-reported outcome data, and participants will be asked to wear an accelerometer for one week. We will allow a window of 3 weeks, to allow flexibility of scheduling such in-person appointments in Boston (and to allow coordination with other medical visits at MGH) while maintaining integrity of study findings. Follow-up assessments will be completed by a study staff member who is blinded to the participant's study condition.

B. Drugs to be used

There are no drugs used in this study.

C. Devices to be used

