- For self-reported physical activity, we will use the IPAQ, well-validated in diverse settings.
- For self-reported smoking history, we will use the Cigarette Use Questionnaire.
- For self-reported alcohol use, we will use the Alcohol Use Disorder Identification Test – Consumption (AUDIT-C).

Medical outcomes (*Aim #3; exploratory*). At baseline and follow-up, we will also measure weight and A1C.

Table 1. Schedule of study events/assessments.

	Pre-enrollment	Enrollment	Weeks 1-8	Week 8	Week 16
Assessment for inclusion criteria (T2D, IPAQ)	X				
Assessment for exclusion criteria (e.g., cognitive screen, other medical conditions limiting activity)	X				
Interview and chart review for baseline characteristics		X			
Self-report measures		X		X	X
Vital signs (weight) and A1C*		X		X	
Accelerometer (MVPA and sedentary time)		X		X	X
PP-MI exercise sessions			X		
Session ratings by participants (ease/utility)			X		

*Will use values from clinical visit (or within 3 weeks in the case of A1C) if available.

VI. Biostatistical analyses:

A and B. Specific data variables and study endpoints

Specific Aim 1 (*feasibility and acceptability*): To determine whether the PP-MI intervention is feasible (assessed by % of total PP-MI phone sessions completed) and well-accepted (assessed by participant ratings of the ease and utility of each PP-MI session) among T2D patients with low baseline activity.

Measures:

- Rates of completion of exercises (recorded by study trainer)

Specific Aim 2 (physical activity): To assess whether PP-MI is associated with larger increases in MVPA, and less sedentary time, on accelerometer at 8 and 16 weeks, compared to MI.

Measures:

- MVPA in mean minutes per day
- Sedentary time in mean minutes per day

Specific Aim 3 (additional outcomes): To explore whether the PP-MI intervention is associated with greater improvements on other psychological, behavioral, and medical outcomes, compared to MI.

Measures:

- Psychological measures: PANAS, LOT-R, SEE, HADS, BRS, MSPSS
- Behavioral measures: SDSCA, % medication adherence, IPAQ, PF-20, PDI
- Medical outcomes: Weight, BMI, and A1C

C. Statistical methods

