Blood sampling. We will obtain A1C data at baseline and 8 weeks. Risks of venous blood sampling include pain, bruising at the phlebotomy site, and emotional discomfort from the process. More rarely, participants may become lightheaded or experience syncope, or have an infection at the site. We will minimize these risks by: (1) ensuring that blood samples are drawn by study staff who have received specific training in phlebotomy (TCRC research protocol nurse) and have specific experience with this procedure, and (2) if A1C is drawn at the clinical visit or was obtained within the prior 3 weeks, that value will be used rather than subjecting the participant to an additional blood draw. Procedurally, we will make sure participants are seated comfortably during and after the sampling, and we will temporarily (or permanently) halt blood draws if patients voice pain or discomfort. If participants experience problems after blood draws (e.g., concerns about infection), they will be able to reach a study physician at any time, who can help to assess the situation over the phone or arrange to have the participant seen by their own physician or by study physician staff to assess any problems.

B. Drug side effects and toxicities

No medications are being used in this study.

C. Device complications

Accelerometer. The devices used to measure physical activity should pose minimal risk to subjects. The accelerometer (ActiGraph G3TX+) used to measure activity as a formal study outcome is small, lightweight, and without sharp edges. Immersing the device in water for a prolonged period may render it unusable, but does not pose a shock risk. We will provide explicit instructions regarding the use of this device to ensure safety and proper use, and to reduce inconvenience/distress associated with uncertainty about their use. Participants will also have study staff contact information if they have questions about the devices; project staff will be well-versed in the use of these devices given their experience from our prior projects that have used the G3TX+.

D. Psychosocial risks

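### The 3-week A1C look-back is not limited to baseline, so a value drawn before the last two or three calls can stand as the 8-week outcome (minor, cheap to fix)

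*Combined protocol and SAP*

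**What the plan says.** Three places set out the look-back.

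- **Section V.A, Initial/Enrollment Visit**, words it for enrollment: "if they had A1C in the last 3 weeks, including this visit, we will use that value to prevent subjecting participants to the blood draw".
- **Section VII.A, Blood sampling**, opens with "We will obtain A1C data at baseline and 8 weeks" and then states, as a way to limit venipuncture risk, that "if A1C is drawn at the clinical visit or was obtained within the prior 3 weeks, that value will be used". Nothing there limits it to baseline.
- **Table 1 (section V.E)** puts an asterisk on the row "Vital signs (weight) and A1C", which is marked at Enrollment and at Week 8. The footnote reads "Will use values from clinical visit (or within 3 weeks in the case of A1C) if available".

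Two places describe the follow-up A1C without mentioning a look-back. Section V.A, Follow-up assessments, says "At this session, height and weight, hemoglobin A1c, and self-report data will be obtained". Section V.D plans a venous sample by study staff at both time points.

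On timing, section V.A says "Following visit #2, participants will engage in weekly, 30-minute phone calls for the next 8 weeks", and then "After completion of the intervention, participants will wear the Actigraph accelerometers for 1 week" before the in-person visit. A 3-week window is allowed for follow-up, with no direction stated. Section VI.C analyses A1C under Aim 3 as change from baseline at 8 weeks, and also reports a pre-post Cohen's d for PP-MI on each Aim 2/3 outcome.

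**The concern.** A baseline value that is up to 3 weeks old still precedes the intervention, so the rule costs nothing there. At follow-up the same rule can replace a post-intervention sample with one drawn while calls are still running. A1C accumulates slowly, so an earlier sample carries less of any effect. No section requires the follow-up A1C to be drawn after the last call, and no adjustment or sensitivity analysis for draw date is described.

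Two Aim 3 summaries are exposed: the between-group comparison of A1C change, and the within-arm Cohen's d for PP-MI. Applying the rule equally in both arms does not protect the second.

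**Working it through.** The plan states no figure on this point, so there is nothing to reproduce. The check has two parts.

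**1. Dates.** Week 0 is in-person visit #2 and the calls fall at weeks 1 to 8 (section V.A). Earliest usable A1C week = visit week − 3.

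| Follow-up visit | Earliest accepted A1C | Calls done by then | Calls left |
|---|---|---|---|
| Week 8 (nominal) | 8 − 3 = week 5 | 5 of 8 | 3 |
| Week 9 (8 calls, then 1 week of wear) | 9 − 3 = week 6 | 6 of 8 | 2 |
| Week 11 | 11 − 3 = week 8 | 8 of 8 | 0 |
| Week 12 | 12 − 3 = week 9 | 8 of 8 | 0 |

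The exposure exists for visits at about week 8 or 9 and is gone by week 11.

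**2. Size for one substituted participant.** The documents give no A1C kinetics. I assume linear red-cell age weighting, w(a) = (2/L)(1 − a/L), with lifespan L of 90 to 120 days. Two effect shapes bracket the answer.

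*Step:* glucose changes fully at week 0. The share of the final A1C change visible at day t is F(t) = 2t/L − (t/L)².

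*Ramp:* the glucose effect builds linearly over T = 56 days. With H(t) = t²/L − t³/(3L²), the share is H(t)/56 up to day 56, and [H(t) − H(t − 56)]/56 after that.

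Example, step, L = 90:
- Week 5 (day 35): 70/90 − (35/90)² = 0.627.
- Week 8 (day 56): 112/90 − (56/90)² = 0.857.
- Loss: 1 − 0.627/0.857 = 27%.

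Each cell below gives L = 90 / L = 120.

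| Shape | Substitution | Share at early draw | Share at visit | Loss, value exactly 3 weeks old | Mean loss, draws even over 3 weeks |
|---|---|---|---|---|---|
| Step | Week 5 for week 8 | 0.627 / 0.498 | 0.857 / 0.716 | 27% / 30% | 12.4% / 14.5% |
| Step | Week 6 for week 9 | 0.716 / 0.578 | 0.910 / 0.774 | 21% / 25% | 9.7% / 12.1% |
| Ramp | Week 5 for week 8 | 0.212 / 0.165 | 0.493 / 0.394 | 57% / 58% | 30.0% / 30.8% |
| Ramp | Week 6 for week 9 | 0.296 / 0.232 | 0.594 / 0.480 | 50% / 52% | 25.5% / 26.6% |

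The last column averages the visible share over the 21 days before the visit and divides by the share at the visit. It is about half the worst case throughout.

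**3. Arm level.** Arm-level dilution = proportion substituted × mean loss per substituted participant. The documents give no proportion. Purely as an illustration, suppose 10% to 20% are substituted with draws spread evenly:
- Step: 0.10 × 9.7% = 1.0% up to 0.20 × 14.5% = 2.9%.
- Ramp: 0.10 × 25.5% = 2.6% up to 0.20 × 30.8% = 6.2%.

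**The case against.** The look-back is a deliberate and stated measure to spare blood draws. Section V.A words it for the enrollment visit, and sections V.A and V.D plan a study draw at follow-up. A1C is labelled exploratory in section V.E, and section VI.D says that the trial is not powered for Aim 2/3 outcomes. On the same assumed kinetics, a sample drawn at week 8 shows only 39-86% of the final change, so the short follow-up limits A1C more than occasional substitution does. The per-participant losses are worst cases and need a chart value near the 3-week limit. All of this stands and keeps the point minor. It does not remove it, because section VII.A and Table 1 as written cover the 8-week value.

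A reader might go further in four ways that the documents do not support.

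- **Between-arm bias.** The rule is the same in both randomised arms, and nothing suggests that substitution would differ by arm.
- **A contradiction within the protocol.** The follow-up paragraph can be read as the general schedule, and the footnote and section VII.A as an exception to it. The passages are unreconciled, not incompatible.
- **A link to disease control.** It is tempting to suppose that patients with unstable glycaemia have more recent clinic A1Cs. The documents contain nothing on this.
- **The same fault for weight.** The 3-week allowance is stated only for A1C, and section V.A has weight measured at the follow-up visit. There is no effect to size.

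**Conclusion.** The point holds as a minor one. As written, the look-back applies at the 8-week follow-up, and for visits at about week 8 or 9 it admits an A1C drawn before the last 2 or 3 of 8 calls.

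For a substituted participant, the worst-case loss is 21-30% of the visit-time A1C change under a step effect, or 50-58% under an 8-week ramp. It is about half that when draw dates are spread evenly. These figures rest on the assumed linear red-cell weighting with a lifespan of 90 to 120 days, and on a visit at week 8 or 9.

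The expected consequence is some dilution of the A1C change and of the PP-MI Cohen's d, plus timing noise. Its arm-level size cannot be computed without a substitution rate and is probably small. The primary feasibility and acceptability aim and the accelerometer outcomes are untouched.

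**What to change.** In section VII.A and the Table 1 footnote, limit the look-back to baseline. At follow-up, accept a clinical A1C only if it was drawn after the final intervention call and within the visit window, and otherwise use the study draw already planned. Bring the follow-up paragraph of section V.A and section V.D into line with this wording, and state the direction of the 3-week visit window. Record the actual A1C draw date for every value analysed.

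The cost is a wording change, one date field, and a few venipunctures that the current rule would have spared, each at a visit the participant already attends. A same-day clinic draw at follow-up could still be used.

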able to participate in a physical activity promotion program prior to approaching the patient. For those who enroll in the program, we will discuss the patient again with the clinician. Specifically, for participants in either condition, we will describe to the clinician the plan for setting goals to increase physical activity, and will ask if there are any specific instructions or cautions to be conveyed to participants, including specific warning signs such as atypical presentations of angina that may be common in T2D patients, such as dyspnea or nausea. This information will be recorded in the REDCap system so interventionists can use this information when developing plans with the patient at phone sessions. If participants have concerning symptoms, interventionists will contact the study physicians (e.g., [name]), who will reach out to the participant's clinician to inform them, obtain direction, and alter the physical activity plan as needed; she will also reach out to participants as needed. As noted above, participants will sign a release of information to allow such contact with clinicians (diabetologist, primary care physician) during the informed consent process.

Depression/anxiety symptoms and suicidal ideation. Participants will complete the Hospital Anxiety and Depression Scale (HADS)⁹³ as part of assessments; although this is a symptom measure and is not used to make a diagnosis of depression or an anxiety disorder, for participants with HADS depression or anxiety subscale scores of 10 or more, we will complete an assessment for suicidal ideation using our standardized, published protocol¹⁰⁵ and inform patients' primary providers of the elevated depression/anxiety score. For participants who have active suicidal ideation or are otherwise considered to be at high risk (e.g., due to combinations of depression symptom severity, history of prior attempt, and passive suicidal ideation), a study psychiatrist will perform a separate assessment and will arrange for urgent evaluation (e.g., in an emergency department) if clinically indicated.

We will ask subjects to report adverse events related to study participation they may have experienced at any time throughout the study. Any adverse events will be reported to the PI and to the IRB according to Partners HRC guidelines.

VIII. Potential benefits

A. Potential benefits to participants

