Serious Adverse Events. Expedited review will occur for all events meeting the definition of Serious Adverse Events (SAEs); i.e., any fatal event, immediately life-threatening event, permanently or substantially disabling event, or event requiring or prolonging inpatient hospitalization. This also includes any event that a study investigator or the DSMB judges to impose a significant hazard, contraindication, side effect, or precaution. All relevant information will be reported to the DSMB for each SAE including information about the event and its outcome, study group assignment, medications, the subject's medical history and current conditions, and any relevant laboratory data. Notification by e-mail and FAX transmittal of all related study forms shall be made to the DSMB. Information will be reviewed and a determination made of possible relevance to the study.

Non-Serious Adverse Events. At periodic intervals determined by the DSMB (e.g., quarterly during the study and then again at its completion), the DSMB will be provided with unblinded summaries of the numbers and rates of adverse events by treatment group. These reports will include types of events, severity, and treatment phase. Data on individual non-serious adverse events is not expected to be needed for this review.

Other Safety-Related Reports. At quarterly intervals, the DSMB will also receive unblinded summary reports of treatment retention and reasons for drop-out, by treatment arm and study phase.

Study Stopping Rules. If at any time during the course of the study, the DSMB judges that risk to participants outweighs the potential benefits, the DSMB shall have the discretion and responsibility to recommend that the study be terminated.

Monitoring of Data Quality by the DSMB. At least on a quarterly basis during the course of the study, the DSMB will receive a report on data quality and completeness. [name] (study biostatistician) will prepare these reports in collaboration with [name]. At a minimum, this will include an overview of the progress of patient intake and retention; summary reports describing patient compliance with evaluations as described in the protocol; and a summary of the completeness and quality of key data elements needed to characterize patients,

study interventions, and primary and secondary outcomes. These reports will be used by the DSMB to evaluate the capacity of the data capture and processing to support scientifically valid analyses.

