Annual DSMB Report to NIH/NIDDK. During the course of the study, the DSMB will prepare annual summary reports (two reports in total) of its findings regarding safety and quality based on data received to that point in the study. If there are more specific concerns about data quality, study safety, or other issues, the DSMB can elect to generate reports more frequently. This report will include a summary of all safety findings, as well as an assessment of protocol compliance and data quality. Any recommendations to improve patient safety, protocol adherence, or data quality will be made in this DSMB report. A copy of this DSMB report will also be sent to the PHS IRB along with the annual renewal report.

In addition to the work of the DSMB, the research team will meet on a weekly basis to review study progress. During these weekly meetings, the principal investigator will review informed consent documents, study forms, and procedures completed that week. The study team will also discuss any procedural difficulties, recruitment issues, and adverse events at this meeting (and before if needed). If there are consistent issues with the logistics, feasibility, or acceptability of recruitment, enrollment, follow-ups, or the intervention (e.g., participant complaints about length of follow-ups), we will review our methods and alter the study protocol as needed.

Patient Alert System. MGH has an electronic system that lets the study team know if a participant is admitted to a Partners Hospital, or if they visit a Partners Hospital Emergency Department for any reason. This alert will let the study doctors know why a participant is there, to make sure the study doctors know about any possible problems or side effects participants experience while taking part in the study.

C. Outcomes monitoring

For this initial randomized pilot trial, we will not plan to perform interim analyses beyond the analyses performed by the DSMB. However, given the feasibility and acceptability focus of this study, we will review ratings of intervention ease/utility after 10 and/or 20 participants if our weekly team meeting reviews suggest that there are substantial barriers to acceptability (e.g., reports from participants at follow-ups/interviews, high rates of dropout) and consider changes to the protocol as indicated.

D. Adverse event reporting guidelines

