We will follow all PHRC guidelines with respect to reporting unanticipated problems, including adverse events. Specifically, when a serious or nonserious adverse event occurs, the PI will review the event to determine if it was possibly or definitely related to participation in the research. For all unanticipated problems and adverse events deemed related or possibly related to the research, we will complete and submit an Other Event report through Insight/eIRB as soon as possible and within 5 working days / 7 calendar days (as defined in the March 2014 Reporting Unanticipated Problems Including Adverse Events report). At Continuing Review, we will provide a summary of all unanticipated problems as per PHRC protocol. Finally, if there are unanticipated problems, especially if serious or recurrent, the PI ([name]) will amend the protocol if it is deemed necessary to protect the safety and welfare of the participants.

X. References

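### The plan's one general adverse event question asks participants to judge relatedness themselves, so events outside the other capture routes may be missed

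*Combined protocol and SAP*

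**What the plan says.** Section VII.D closes with the instruction on eliciting events: "We will ask subjects to report adverse events related to study participation they may have experienced at any time throughout the study". The next sentence deals with onward reporting: "Any adverse events will be reported to the PI and to the IRB according to Partners HRC guidelines".

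The Monitoring and Quality Assurance section then sets out who judges and who reviews. Under D (Adverse event reporting guidelines), for serious and non-serious events alike, "the PI will review the event to determine if it was possibly or definitely related to participation in the research". Under B (Safety monitoring), every serious adverse event gets expedited DSMB review. For non-serious events, at intervals such as quarterly, "the DSMB will be provided with unblinded summaries of the numbers and rates of adverse events by treatment group". Neither DSMB review is restricted to related events.

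Table 1 (section V.E) has no row for adverse events, and no section describes a general question put at scheduled contacts without reference to cause.

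**The concern.** Relatedness is a judgement for someone who has the event in front of them. The general question puts it one step earlier, with the participant. An event that the participant does not connect with the programme is not asked for, so the PI may have nothing to assess and the DSMB nothing to count.

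At stake is the completeness of the safety counts, mainly for non-serious events, and whether those counts can be compared between arms. Participants are not blinded, and the two programmes differ in how directly they push activity. The habit of linking an ache or a fall to the study could therefore differ between arms. If so, a low or unequal count could not be told apart from incomplete or unequal reporting.

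**Working it through.** The documents give no adverse event rate and no safety sample-size figure, so there is nothing to reproduce. The check is a comparison of what is elicited with what is to be reviewed.

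**Step 1: scope of each stage.**
- Elicitation (VII.D): events the participant regards as study-related.
- Onward reporting (VII.D, next sentence): any event, but necessarily one already known to staff.
- Relatedness (Monitoring, D): decided by the PI after an event occurs.
- DSMB review (Monitoring, B): all serious events, plus counts and rates by arm for the rest.

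The first stage is narrower than the three that depend on it. The second cannot widen it, because it acts on events that have already surfaced.

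**Step 2: routes that do not depend on the participant's attribution.**
- Hypoglycemia (VII.D): signs and symptoms are queried at all calls and follow-ups for participants on predisposing medications. The others are encouraged to volunteer any such symptoms.
- HADS (VII.D): a depression or anxiety subscale score of 10 or more triggers a staff assessment.
- Concerning symptoms (VII.D): interventionists escalate these to study physicians. No structured question is given.
- Urgent medical or psychiatric conditions apparent at sessions or follow-ups (VII.D): assessed by a study physician.
- Symptom monitoring during activity progression (V.A, MI component of PP-MI): stated for PP-MI, with no content specified.
- Patient Alert System (Monitoring, B): "MGH has an electronic system that lets the study team know if a participant is admitted to a Partners Hospital". Emergency attendances within Partners are flagged too, whatever prompted them.

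**Step 3: what remains.** Falls, musculoskeletal injury and similar problems managed outside hospital are covered only if the participant mentions them or links them to the study. The same applies to serious events treated outside Partners hospitals. After the weekly calls end, the only scheduled contacts described are the 8-week visit and the 16-week phone assessment, so the wording of the question matters most there.

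**Step 4: could the gap differ by arm?** Participants learn their condition (IV.C). A completed PP-MI session must end with a specific activity goal (V.E), whereas the control is described as lacking such goal-setting (V.A). Symptom monitoring is stated for PP-MI and has no counterpart in the control description. In general:

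observed rate ratio = true rate ratio × (share of events captured in PP-MI ÷ share captured in control).

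The documents give neither share. The second factor could be 1, or lie on either side of it.

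**The case against.** The strongest reply is that the plan, read as a whole, does not intend to exclude unattributed events. The sentence after the question sends any event to the PI, and the PI's review covers serious and non-serious events. For participants in either condition, clinicians are asked for cautions and warning signs, including atypical angina. These are recorded for use at phone sessions, and concerning symptoms are escalated whatever cause the participant gives. This is a behavioral pilot of 60 people with no study drug, and section VII.D deliberately limits symptom questions to spare participants.

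Much of this stands. A reader might infer that the participant's judgement filters all events, or that symptom queries are confined to hypoglycemia. The routes in Step 2 show otherwise: Partners admissions and emergency visits are flagged whatever the reason, and chest symptoms have a described path to the study physicians.

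A reader might also infer that the by-arm comparison is biased, with PP-MI over-reporting relative to control. The documents do not support that either. Control sessions 4 to 6 are about physical activity, all participants receive pedometers, and patients are told at recruitment that the study aims to improve physical activity. Controls therefore also have reason to connect an activity injury with the study. The contrast in goal-setting makes unequal ascertainment possible but does not establish it.

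What the reply does not remove is the mismatch itself. None of these provisions asks a participant, in general terms, about events whatever their cause.

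**Conclusion.** The concern holds in a limited form. The plan's single general question asks participants to pre-judge a decision assigned to the PI, and it is narrower than the DSMB review it feeds. The exposure is confined to events outside the routes in Step 2: chiefly non-serious, non-hypoglycemic problems managed outside hospital, and serious events treated outside Partners. Those counts may be incomplete.

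The size of any shortfall cannot be derived, and neither the size nor the direction of any difference between arms can be. Any number would rest on assumed reporting shares. The conclusion assumes that staff would ask the question as the plan words it, and that no unreported procedure already puts an open question at each contact.

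The change is worth making because it is cheap and the DSMB relies on these counts. The Aim 1 to 3 analyses and the power statement are untouched.

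**What to change.** Replace the VII.D sentence with a rule along these lines: in both arms, with the same open question, participants are asked at scheduled contacts about any new or worsened health problem since the last contact, whatever they think caused it. The minimum is the 8- and 16-week assessments; the existing weekly calls are preferable as well. Leave relatedness to the PI, as the adverse event reporting guidelines already provide. Add an adverse event row to Table 1, and align VII.D with Monitoring B and D so that elicitation, assessment and DSMB review have the same scope.

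Cost: no new contacts. At the two follow-ups alone, the question is asked at most 60 × 2 = 120 times; with the eight weekly calls, at most 60 × (8 + 2) = 600 times. Contacts become slightly longer, and more unrelated events must be logged and reviewed by the PI. If that burden is judged too high for the weekly calls, the two-assessment minimum still removes the attribution filter from the question.
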